6. STATISTICAL DESIGN AND POWER

6.1 Sample Size

Objective 1: Sample size is based on estimates of receiving a molecularly-informed treatment recommendation at the initial oncology visit. Based on our prior studies, we anticipate this will occur in 10% of patients in the usual care arm. This pilot study is designed to detect an absolute increase of 20% in our primary outcome for patients in the intervention arm. With a sample size of 124 participants and a two-sided alpha, we will have >80% power to detect an increase of this magnitude. Given the potential for drop-out of patients following randomization, we have increased the estimate by 10%, leading to a final sample size of 138 participants (69 in each arm). Although a difference <20% in our primary outcome rate may be clinically meaningful, this sample size is an optimal balance to allow an assessment of our primary and secondary outcomes and assess for mechanisms of action. Study outcomes will be used to preliminarily assess effectiveness across all outcome domains to inform the design of future studies, including a pragmatic trial, if warranted.

Objective 2: Proposed sample size is based on the estimated number of interviews needed to reach data saturation within each group and by intervention outcome to support mixed methods evaluation; however, interviews will continue until saturation is achieved.^{16,21}

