6.2.3 Objective 1 Exploratory Analyses

[figure not shown]
A difference in effectiveness of the telehealth intervention for Black versus White patients will be conducted by adding a main effect of race and the interaction of race and intervention to the primary unadjusted logistic regression model. Given that hypothesis tests of interaction terms are likely severely underpowered at our pilot study sample size, we will focus statistical inference on the point estimate and 95% confidence intervals for the interaction term. While these intervals may cross the null value consistent with no difference in effectiveness, confidence intervals that largely lie away from the null provide evidence in favor of differential intervention effects that could be detected statistically with a larger sample size in a subsequent study. Patients who do not identify as Black or White will be excluded from this analysis.

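### Section 6.2.3 lets a race-by-arm confidence interval that includes the null count as evidence of a differential effect, with no cut-off, so the planning signal it yields could often be chance

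*Combined protocol and SAP*

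**What the plan says.** Section 6.2.3 (Objective 1 Exploratory Analyses) compares the effect of telehealth navigation in Black and White patients by "adding a main effect of race and the interaction of race and intervention to the primary unadjusted logistic regression model". It says that a test of this term would probably be severely underpowered in a pilot, so "we will focus statistical inference on the point estimate and 95% confidence intervals for the interaction term". It makes a concession: "While these intervals may cross the null value consistent with no difference in effectiveness". Its rule for reading such results is nevertheless that "confidence intervals that largely lie away from the null provide evidence in favor of differential intervention effects". The sentence ends by describing those effects as ones that a larger follow-on study could detect. Patients who identify as neither Black nor White are left out.

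The section gives no share or cut-off for the rule, no error rate, no projected number of Black and White patients, and no fallback if the model cannot be fitted.

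**The concern.** An interval that contains the null is compatible with no difference between the races. Under this rule it can still be reported as evidence of a difference, provided enough of it falls on one side. How much is enough would be judged after the data are seen. If chance meets the rule frequently, meeting it says little.

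Equity is one of the endpoint domains in Section 5.4 and part of the rationale in Section 1. Section 6.1 says the outcomes will inform future studies. A chance pattern, in either direction, could therefore be carried into the planning of later work as though it were an effect waiting for more patients.

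A related weakness is that the inference rests on an estimate and interval that ordinary logistic regression may fail to produce when events are this few.

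**Working it through.** **Inputs from Section 6.1.** Usual care: "we anticipate this will occur in 10% of patients in the usual care arm". Effect: "designed to detect an absolute increase of 20% in our primary outcome", that is 10% versus 30%. Size: "With a sample size of 124 participants and a two-sided alpha, we will have >80% power to detect an increase of this magnitude". Allocation is 1:1, so 124 evaluable patients means 62 per arm. The value of alpha is not printed; 0.05 is assumed.

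**The plan's own figure.** Pooled-variance formula, no continuity correction: n per arm = [1.96 × √(2 × 0.20 × 0.80) + 0.842 × √(0.10 × 0.90 + 0.30 × 0.70)]² / 0.20² = (1.109 + 0.461)² / 0.04 ≈ 61.6, so 62 per arm and 124 in total. Power at 62 per arm is 80.3%. Then 124 / 0.90 = 137.8, so 138. The stated sample size reproduces and is not in dispute.

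**Assumptions not in the documents.** The share of Black patients in the trial is not given; 20-40% is used. (The oversampling of Black patients in Sections 4.2 and 5.1 concerns the interviews only.) All 124 evaluable patients are taken to be Black or White. Under the null, event rates within each arm are the same in both races.

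**Chance of meeting the rule with no interaction.** For a symmetric 95% interval on the log-odds scale, at least a share f lies on one side of the null when the absolute z is at least 1.96 × (2f − 1). The probability is 2 × [1 − Φ(1.96 × (2f − 1))]. The simulated column comes from the four-cell model at N = 124, 10% versus 30%, with 200,000 runs per scenario. Its range covers Black shares of 20-40% and two treatments of sparse cells: adding 0.5 to every cell, or keeping only trials with no empty or full cell.

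| Share of interval required on one side | Absolute z needed | Normal theory | Simulated |
|---|---|---|---|
| two thirds | 0.653 | 51% | 45-50% |
| 75% | 0.980 | 33% | 26-30% |
| 80% | 1.176 | 24% | 18-21% |
| 90% | 1.568 | 12% | 7-8% |
| 100% (interval excludes the null) | 1.960 | 5% | 2-3% |

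The simulated rates are lower because Wald intervals are conservative with few events. If telehealth has no effect (10% in both arms), they fall further, to 17-29% at a 75% share, 11-21% at 80% and 3-7% at 90%, against 1-2% for an interval that excludes the null. Every cut-off still exceeds the rate for an interval that excludes the null.

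**What meeting the rule would tell us.** The variance of the log interaction odds ratio is the sum over the four cells of 1/[n p (1 − p)]. At a 20% Black share (12.4 and 49.6 per arm): 0.896 + 0.384 + 0.224 + 0.096 = 1.600, SE 1.265. At 40% the SE is 1.033. The interval therefore extends by a factor of exp(1.96 × 1.033) ≈ 8 to exp(1.96 × 1.265) ≈ 12 on each side of the estimate. For a true interaction odds ratio of 2, normal theory gives the 80% reading as met in the right direction 26.5-30.7% of the time and in the wrong direction 4.2-3.2%, together 31-34%. With no interaction it is met 24% of the time.

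**Empty or full cells.** With 12 Black usual-care patients (20% share), P(no events) = 0.9¹² = 28%; with 25 (40% share), 0.9²⁵ = 7%. Counting all four cells, some cell is empty or full in 1 − (1 − 0.9¹²)(1 − 0.7¹²)(1 − 0.9⁵⁰) ≈ 30% of trials at a 20% share, and 9% at 40%; full cells are negligible. The simulation agrees (29.6%, 14.6% and 9.0% at 20%, 30% and 40%).

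**The case against.** The strongest defence is context. The analysis is labelled exploratory, the low power is admitted, and the sentence acknowledges that such an interval may be consistent with no difference. It then ties the evidence to a later, larger study. Read whole, it describes a planning signal, and because the estimate and interval will be reported, readers will see any interval that crosses the null. All of this stands and limits the severity. It does not rescue the rule: with no true interaction, a larger study would find one only at its own error rate.

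A reader might infer more than the text supports:

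- *That the trial would announce a racial difference in effect.* The final clause of the sentence points to later study, so this goes too far.
- *That this result decides whether a later study examines race.* Section 6.1 speaks only of informing future designs, and Section 6.2.3 has no go/no-go step.
- *That a 5% interaction test has been replaced by a weaker one.* No such test was planned; the section declines to rely on testing.
- *That the normal-theory rates are what this trial would see.* They are too high for cells this sparse. At a 90% cut-off the simulated rate of 7-8% is not far above a nominal 5%.

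Two technical objections also have force. An empty cell does not make inference impossible, since exact or profile-likelihood methods can still give a one-sided bound, and the plan does not commit to Wald intervals. But the plan rests its inference on a point estimate, which would be infinite, and names no alternative method. Second, nothing here shows the odds-ratio scale to be wrong. It matches the primary model in Section 6.2.1, and moving to a difference in risk differences would be a preference.

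**Conclusion.** The concern holds as a minor one. As written, the rule allows an interval containing the null to be called evidence, on a cut-off left undefined. For the design's own rates at 62 per arm, chance alone would meet it in roughly a fifth to a half of trials for cut-offs from 80% down to two thirds of the interval, and in 7-8% at 90%, against 2-3% for an interval that excludes the null. Whether *often* is the right word depends on how *largely* is read; that the rule raises the false-signal rate does not.

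Separately, about 9-30% of trials would have a race-by-arm cell for which ordinary logistic regression gives no finite interaction estimate.

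These figures rest on alpha 0.05, an assumed Black share of 20-40%, 124 evaluable patients all Black or White, and no true interaction. Excluding other patients would shrink the cells; analysing all 138 would enlarge them slightly. The primary comparison, the sample size and the conduct of the trial are unaffected.

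**What to change.** In Section 6.2.3:

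1. Delete the sentence that treats intervals lying mostly to one side of the null as evidence.
2. State that the interaction estimate with its 95% interval, and the event rates by arm and race, will be reported as descriptive and hypothesis-generating, and that an interval containing the null does not establish a differential effect.
3. Fit the interaction model with Firth penalisation and a profile-likelihood interval, so that an empty cell does not break it. This keeps the estimate finite; it does not add information, and the interval will stay wide.

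The cost is two or three sentences and no new data. The only loss is that a suggestive pattern can no longer be called evidence; it can still be shown and discussed when a later study is planned.

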6.2.4 Objective 2 Analyses

We will descriptively assess survey data and thematically code interview data. These data will be used to conduct qualitative comparative analysis (QCA) to identify how contextual factors shaped both timeliness and quality of care and the effectiveness of nurse navigation. QCA is a multistep analytic method that combines qualitative and quantitative coding and calibration to identify conditions shaping the effectiveness of telehealth strategies.

The four-step process will use survey and interview data as inputs or “conditions.”

Code Contextual Data (Step 1-2). We will use convergent mixed methods analysis to code contextual conditions (inner setting, outer setting, and individual characteristics) and implementation conditions (characteristics of specific telehealth strategy and process).

Qualitative Data. The constant comparative method, guided by modified grounded theory,²² will be used to iteratively identify *a priori* domains of interest (guided by FITE) and to inductively explore emergent themes. Two trained coders will first independently read through each transcript to identify themes within each domain. We then will use this list to develop a coding dictionary and apply it to the data. We will measure inter-rater reliability to document and improve coding consistency. Once high reliability is achieved (kappa >0.8), we will apply the full coding dictionary to the interview data using NVivo and produce thematic reports summarizing our findings. We will then use qualitative data to expand upon and triangulate quantitative patterns identified in trial and surveys.²³

Survey Data. Survey data will be analyzed descriptively and coded dichotomously or categorically as appropriate. Contextual data will serve as QCA inputs to identify necessary and sufficient conditions for telehealth success.

Qualitative Comparative Analysis (QCA) (Steps 3-4). For QCA, our primary endpoint will be receipt of a molecularly-informed treatment recommendation at the time of the patient's initial in-person oncology visit, and success or failure will be determined at the patient level. Each case will be calibrated as having or not having the primary outcome or condition (described above).²⁴ Thresholds for coding primary outcomes and the presence or absence of each condition (e.g., low quality communication) will be determined based on existing literature or stakeholder consensus. Most outcomes will be dichotomous, but continuous values and fuzzy set QCA will be used as appropriate.^{27,28} Data ("truth") tables will be created for analysis, which list all possible configurations of conditions, the number of cases that fall into each configuration, and the consistency of the cases—or the proportion of cases in the specific configuration that have the desired outcome.^{28,29} We will conduct QCA analyses using R package *QCAPro*.³⁰⁻³² Raw and unique coverage will be calculated and consistency will be set at 80% for sufficient and 90% for necessary conditions. This iterative analytic process will identify what conditions—alone or in combination with others—are necessary or sufficient to yield the primary endpoint.

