4.4 Study Setting

This study will occur within the University of Pennsylvania Health System (UPHS). Research activities will be conducted at the following UPHS sites:

- Hospital of the University of Pennsylvania Pavilion (HUP) – East
- Hospital of the University of Pennsylvania (HUP)
- Pennsylvania Hospital (PAH)
- Penn Presbyterian Medical Center (PPMC)

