Objective 2: We will use structured and validated measures and a semi-structured interview guide based on our Framework for Integrating Telehealth Equity (FITE) to systematically evaluate individual and contextual factors (e.g., treatment knowledge, medical mistrust, clinical beliefs, patient-centered communication, financial toxicity, and knowledge of genetic testing) that will shape the effectiveness of telehealth strategies. Domains that will be assessed as part of the Objective 2 include:

- 1) Telehealth usability, acceptance, and satisfaction (using the University of Pittsburgh Telehealth Usability Questionnaire)
- 2) Patient-centered communication (using the University of North Carolina Patient-Centered Communication in Cancer Care Instrument)
- 3) Medical-related trust and mistrust (using the Group-Based Medical Mistrust Scale [GBMMS])
- 4) Acceptability, appropriateness, and feasibility of interventions (using the Acceptability of Intervention Measure [AIM] Intervention Appropriateness Measure [IAM] and Feasibility of Intervention Measure ([FIM]))
- 5) Treatment related knowledge and beliefs
- 6) Other contextual factors (e.g., organizational climate, barriers to using telehealth) that may impact effectiveness of trial

Objective 2 endpoints for the subset of enrolled participants will be assessed up to 1 year from randomization.

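### The QCA labels a condition necessary on 90% consistency alone, a measure that ignores failures, so conditions shared by all or nearly all cases can pass without relating to success

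*Combined protocol and SAP*

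**What the plan says.** Section 6.2.4 (Objective 2 Analyses) sets out a QCA of survey and interview data. The outcome is the trial's primary endpoint, and "success or failure will be determined at the patient level". The inputs are broad: the team will "code contextual conditions (inner setting, outer setting, and individual characteristics) and implementation conditions". Section 5.4 adds a measured domain, "Other contextual factors (e.g., organizational climate, barriers to using telehealth) that may impact effectiveness of trial". Thresholds for coding a condition as present or absent "will be determined based on existing literature or stakeholder consensus".

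The decision rule is one sentence: coverage, both raw and unique, is to be computed, and "consistency will be set at 80% for sufficient and 90% for necessary conditions". No cut-off or use in judging necessity is given for coverage. The section states no relevance or triviality check for necessity, no rule for constant or highly skewed conditions, and no necessity test on the negated outcome.

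Two other places matter. Section 4.4 places the study in one health system and lists four hospitals. Section 5.1 stratifies the 20 to 30 interviewed patients by outcome and arm, with 5 to 10 per stratum, so failures are sampled on purpose.

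**The concern.** A necessary condition is one without which success does not occur. Finding it in nearly all successes is informative only if it is absent from a fair share of failures. The stated rule uses the first half of that comparison and leaves out the second.

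This design makes the gap relevant. Setting-level conditions are inputs, the outcome is judged per patient, and all patients come from one health system. Any factor that is truly common to them takes the same value in every case.

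Objective 2 is listed among the primary objectives. Section 7.5 expects the study to identify conditions that should be targeted or adapted for the strategy to succeed. A condition wrongly labelled necessary would feed into that use.

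**Working it through.** The 90% is a chosen convention, so there is no figure to reproduce. What can be checked is how the rule behaves.

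**Inputs**
- Threshold: 90% (6.2.4).
- Success cases: two of the four outcome-by-arm strata are success strata, each with 5 to 10 patients (5.1), so 2 × 5 = 10 to 2 × 10 = 20. This takes the interviewed patients as the QCA cases.
- Prevalence of each condition: not in the documents. Assumed 80%, 90%, 95% and 100%, and unrelated to outcome.

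**Measures for a condition X, outcome Y, N cases**
- Necessity consistency = n(X and Y) / n(Y).
- Raw coverage of X as a single-condition path = n(X and Y) / n(Y), which is the same ratio.
- Coverage of necessity = n(X and Y) / n(X).
- Relevance of necessity = (N − n(X)) / (N − n(X and Y)).

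**Constant condition.** Here n(X and Y) = n(Y), so consistency is 100% and it always passes. Raw coverage is also 100%, so it gives no warning. Coverage of necessity is only the base rate of success (15/30 = 50%; 10/30 = 33%; 20/30 = 67%), and relevance is (30 − 30)/(30 − 15) = 0.

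**Common but unrelated condition.** With n successes and prevalence p, the chance of passing is P(X ≥ r), X ~ Binomial(n, p), r = 0.9n rounded up. For example, n = 15 gives r = 14, and at p = 0.9 the chance is 15 × 0.9^14 × 0.1 + 0.9^15 = 0.343 + 0.206 = 0.549.

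| Prevalence | n = 10 (r = 9) | n = 12 (r = 11) | n = 15 (r = 14) | n = 20 (r = 18) |
|---|---|---|---|---|
| 80% | 0.38 | 0.28 | 0.17 | 0.21 |
| 90% | 0.74 | 0.66 | 0.55 | 0.68 |
| 95% | 0.91 | 0.88 | 0.83 | 0.93 |
| 100% | 1 | 1 | 1 | 1 |

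Because r is rounded up, the chance dips for some n between these columns. With 17, 18 and 19 successes, r is 16, 17 and 18; the same formula gives 0.48, 0.45 and 0.42 at 90% prevalence, and 0.79, 0.77 and 0.76 at 95%. At 80% the lowest value is 0.08, at n = 19.

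**What a relevance measure would show.** Take 15 successes in 30 cases and expected counts. An unrelated condition at 90% prevalence has n(X) = 27 and n(X and Y) = 13.5, so relevance is 3/16.5 = 0.18. At 80% it is (30 − 24)/(30 − 12) = 0.33. Coverage of necessity is 50% in both, equal to the base rate. These values expose what consistency hides.

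**What the comparison with failures adds.** Require also that the proportion with X be lower among failures. The chance of a false label is then the sum of P(i) × P(j) over i ≥ r successes and j failures with j/n(failures) < i/n(successes). With 15 and 15 cases at 90% prevalence it falls from 0.55 to 0.32; at 95% it falls from 0.83 to 0.31. The comparison helps but does not remove chance passes, which is why relevance should be shown beside it.

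**The case against.** The strongest reply is that the analyst will not see successes alone. Failures are sampled by design. The truth tables list every configuration with its case count and the proportion with the outcome. Surveys are summarised descriptively, and the qualitative data are used for triangulation. A constant column would be visible. That stands as a reason not to say that mislabelling will happen. It does not supply a rule: the truth-table consistency described is a sufficiency measure, and nothing says what to do with a constant or very common condition.

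A reader might infer two stronger things that the documents do not support.
- *That setting factors are constant here.* Four hospitals are listed, and inputs come from individual surveys and interviews. Perceived climate, telehealth barriers or communication can differ between patients of one system. Only a factor truly shared by all cases passes with certainty, and the documents do not show that any particular condition is constant.
- *That any common condition will be labelled necessary.* At 80% prevalence a single unrelated condition usually fails. The chance that at least one of several passes is higher, but it depends on the number, prevalence and independence of the conditions, none of which the documents fix.

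It is also fair that necessity labelling is one output of Objective 2, in a pilot meant to inform later studies.

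**Conclusion.** The concern holds in a limited form. The only stated criterion for necessity ignores failures, and the planned coverage measures do not make up for it. Constant conditions pass with certainty. Unrelated conditions at 95% prevalence pass more often than not for every number of successes from 10 to 20. At 90% they do so for most of those numbers, with the exception of 17 to 19, where the chance is somewhat below one half.

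These figures rest on assumed prevalence, no relation to outcome, and yes/no coding. How many QCA conditions are constant or that common cannot be told from the documents. The point should be addressed because it bears on what Objective 2 may conclude; it does not touch the Objective 1 analyses or sample size.

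**What to change.** In section 6.2.4:
1. Call a condition necessary only if its consistency is at least 90% **and** its frequency among failures is reported and is lower than among successes.
2. Report relevance of necessity (or coverage of necessity, against the base rate of success) next to consistency. If a cut-off is used, set it before analysis.
3. Report conditions that do not vary across cases descriptively, without the label necessary.

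A blanket exclusion of conditions present in more than 80% or fewer than 20% of cases, or a fixed relevance cut-off of 0.6, should not be adopted. Section 5.1 permits 20 successes and 10 failures. A condition in all 20 successes and 5 of 10 failures has prevalence 25/30 = 83% and relevance (30 − 25)/(30 − 20) = 0.5, so either rule would discard it, although failures have it half as often. The lower bound would also drop a condition found in 5 of 30 cases, all successes (5/30 = 17%), which has 100% sufficiency consistency; that would change the sufficiency analysis.

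The cost is a few sentences, with no new data or patients, since failures are already sampled. The downside is that fewer conditions will carry the label, and shared setting factors get only a descriptive account.

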Patients in the intervention arm will be scheduled for an enhanced synchronous telehealth visit with a trained lung cancer nurse navigator prior to tissue biopsy. The enhanced synchronous telehealth visit will ideally occur between the initial clinical appointment and diagnostic biopsy (typically a period between two and seven days). In addition to the activities conducted as part of usual care, the nurse navigator will: 1) provide more detailed and individualized education on lung cancer and the rationale for comprehensive molecular testing, including plasma-based tests; and 2) if the patient agrees to testing, pend a default order for plasma-based molecular testing (if not already ordered) for the clinician to sign and arrange for phlebotomy to be performed during the periprocedural window associated with the patient's tissue biopsy.

Objective 2: Using rigorous approaches proven successful in our prior work,^{15,16} we will recruit 20-30 patient participants of the primary trial and 10-15 clinicians and clinical leaders to complete semi-structured interviews following the active trial period.

Patients: We will oversample for Black patients to understand effectiveness by race/ethnicity and stratify by trial outcome and study arm to understand factors contributing to both success and failure (e.g., primary endpoint) in either group (5-10 patient in each stratum). Trial participants will be invited in randomly selected batches each month (to enhance capture over time) until we reach our target sample of approximately 20-30 patients. Patients will be invited to participate in interviews via email and/or letter within 6 weeks of their in-person oncology visit.

Clinicians: Recruitment for clinicians will be similar to the procedure for patients, except we will wait until the completion of the full trial to conduct interviews to avoid potential contamination. Clinicians will be purposively sampled by clinical role (e.g., oncologists, nurses, clinical leads) to enhance variation and invited via email. Recruitment will continue until we reach our target sample of 10-15 clinicians.

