4.3 Study Duration and Timeline

The study duration will be approximately 30 months. In months 1-3 we will conduct rapid-cycle approaches (RCAs) to optimize the telehealth navigation intervention.

Objective 1: In month 3, we will launch the study and randomize patients by study arm. The active trial enrollment period will be approximately 18 months in length to reach the estimated sample size of 138 patients. Longitudinal data capture to collect secondary outcome information for patients will be completed up to 1-year post-enrollment. Collection and verification of all study endpoints will be completed by 30 months after the study's start date.

Objective 2: Invitations for surveys and qualitative answers for patients will be sent within 6 weeks of the in-person oncology visit and will be completed within 3 months of invitation. Clinician and clinical leader interviews will be completed between months 15 and 21 of funding. Mixed methods analysis for Objective 2 will run from months 18-24.

An overview of the project timeline is below.

Table 1. Trial Timeline

Project Timeline	2023				2024				2025			
	Q1	Q2	Q3	Q4	Q1	Q2	Q3	Q4	Q1	Q2	Q3	Q4
Objective 1: Enroll eligible trial participants		•	•	•	•							
Objective 1: Deliver intervention		•	•	•	•							
Objective 1: Endpoint ascertainment & analysis		•	•	•	•	•	•					
Objective 2: Recruit & conduct patient interviews			•	•	•	•	•	•				
Objective 2: Recruit & conduct clinician interviews								•	•			
Objective 3: Mixed methods coding & analysis									•	•		
Submit manuscripts & disseminate results										•		

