5.4 Measures and Endpoints

Objective 1: The specific outcomes align with 5 key endpoints (access, quality, outcomes, equity, and efficiency). The primary endpoint is receipt of a molecularly-informed treatment recommendation at the time of the patient's initial in-person oncology visit, measured up to 12 weeks from randomization. This outcome encompasses successful completion of comprehensive molecular testing and the ability of the patient and oncology care team to have all necessary information to collaboratively arrive at the optimal treatment approach. We anticipate that approximately 10% of patients randomized to usual care will be able to receive a molecularly-informed treatment recommendation at initial visit – these include patients in whom tissue was successfully tested and identified a targetable mutation prior to referral. We anticipate this will be substantially improved with enhanced nurse navigation (See Section 6.1 Sample Size). The primary endpoint will be assessed by review of clinician documentation (e.g., progress notes) within the electronic medical record (EMR) on the day of the initial visit.

Secondary outcomes include:

- 1) Operational endpoints:
 - a. Rate of completion of telehealth visit defined as successful completion of a nurse navigator telehealth visit prior to biopsy, measured up to 3 weeks from randomization.
 - b. Rate of completion of comprehensive molecular testing (tissue and/or plasma testing) prior to initiation of first line therapy, measured up to 12 weeks from randomization.
- 2) Clinical endpoints:
 - a. Time from randomization to molecularly-informed treatment recommendation, measured up to 12 weeks from randomization.
 - b. Proportion of participants with one or more targetable mutations, measured up to 12 weeks from randomization.
 - c. Overall survival, measured as 1-year overall survival from time of randomization to death from any cause.
 - d. The proportion of enrolled patients with a diagnosis other than metastatic NSq NSCLC (telehealth arm only), measured at 12 weeks from randomization.
 - e. Time from randomization to treatment initiation, measured up to 12 weeks from randomization.
- 3) Cost outcomes:
 - a. Intervention costs (measured using a pragmatic method to capture and analyze all system-level resources, such as personnel time and patient outreach costs) that are needed to deploy telehealth strategies in routine care.¹⁹

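### The QCA treats patient perceptions and knowledge collected after the oncology visit as conditions that yield an endpoint already fixed at that visit

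*Combined protocol and SAP*

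**What the plan says.** Section 6.2.4 defines the QCA endpoint as "receipt of a molecularly-informed treatment recommendation at the time of the patient's initial in-person oncology visit, and success or failure will be determined at the" level of the individual. Section 5.4 says it is read from clinician documentation "within the electronic medical record (EMR) on the day of the initial visit".

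For the explanatory side, section 6.2.4 states: "The four-step process will use survey and interview data as inputs or" conditions. It sorts them into contextual conditions (inner setting, outer setting, individual characteristics) and implementation conditions, and its one worked example of a condition is poor communication. Section 5.4 lists the domains measured, among them telehealth usability and satisfaction, patient-centered communication, medical mistrust, and treatment knowledge and beliefs.

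On timing, section 4.3 says that patient invitations "will be sent within 6 weeks of the in-person oncology visit and will be completed within 3 months of invitation". Section 5.4 sets an outer limit: "Objective 2 endpoints for the subset of enrolled participants will be assessed up to 1 year from randomization". Section 5.1 places the survey before or at the interview and stratifies interviewees by arm and by whether the recommendation was received. No pre-visit patient survey is described.

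The conclusion is directional: the QCA is to identify conditions, alone or combined, that "are necessary or sufficient to yield the primary endpoint", with consistency set at 80% for sufficiency and 90% for necessity.

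**The concern.** An explanatory condition has to be in place before the result it explains. A patient who left the visit with a molecularly-informed recommendation has had test results discussed and a plan agreed. Weeks later that patient may well report better communication, more knowledge and more satisfaction because of it. Entered as a condition, such an answer can look necessary or sufficient for success although it followed from success.

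The protocol itself points this way. Its central hypothesis (section 1) lists better patient-clinician communication and higher satisfaction among the results expected from the navigation. The same section says that barriers to reaching a decision at the first visit reduce satisfaction. Section 2.2 lists communication and treatment knowledge among the Objective 2 outcomes, and section 6.2.4 then uses survey data on such constructs as inputs without a rule on direction.

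Objective 2 concerns mechanisms, section 7.5 expects the results to identify conditions to target or adapt, and section 6.1 says study outcomes will inform future studies. A consequence labelled as a cause would be a poor target.

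**Working it through.** The plan gives no figure of its own on this point beyond the two cut-offs, so the main check is time order.

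**1. When the endpoint is fixed.** On the day of the initial in-person visit (sections 5.4 and 6.2.4).

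**2. When the patient answers are given.** Invitation up to 6 weeks after the visit, plus completion up to 3 months (about 13 weeks) after invitation: 6 + 13 = about 19 weeks after the endpoint is fixed (section 4.3). The endpoint may itself fall up to 12 weeks after randomization (section 5.4), so this schedule ends by about 12 + 6 + 13 = 31 weeks from randomization, inside the 1-year outer window.

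**3. Could the section 4.3 wording include time before the visit?** Taken alone, perhaps. But interviewees are stratified by trial outcome (sections 4.2 and 5.1), so the outcome must be known first. Section 4.2 also describes interviewees as recruited "to complete semi-structured interviews following the active trial period".

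**4. Do the cut-offs protect against reversal?** No. For a single condition:
- necessity consistency = P(condition | success)
- sufficiency consistency = P(success | condition)

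Neither contains time. With equal numbers of successes and failures, and the condition reported by a fraction *a* of successes and *b* of failures, necessity is *a* and sufficiency is *a*/(*a* + *b*).

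**5. Illustration; every rate and the 12/12 split are assumptions.** Suppose 12 successes and 12 failures are interviewed and the condition is purely an effect of the outcome. Let *i* ~ Bin(12, *a*) and *j* ~ Bin(12, *b*). The sufficiency cut-off is met when *i*/(*i* + *j*) ≥ 0.80. The necessity cut-off is met when *i*/12 ≥ 0.90, that is *i* ≥ 11.

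| *a* vs *b* | Sufficiency at these rates | P(meets 80% sufficiency) | P(meets 90% necessity) |
|---|---|---|---|
| 0.50 vs 0.50 | 0.50 | 0.006 | 0.003 |
| 0.60 vs 0.30 | 0.60/0.90 = 0.67 | 0.16 | 0.02 |
| 0.80 vs 0.20 | 0.80/1.00 = 0.80 | 0.55 | 0.28 |
| 0.90 vs 0.10 | 0.90/1.00 = 0.90 | 0.91 | 0.66 |

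For 0.80 vs 0.20, splits from 10 + 10 to 15 + 15 give 0.55 to 0.58 for sufficiency. A strong reverse effect often passes, a moderate one seldom does, and no association almost never does. The table covers single conditions; the plan also assesses configurations.

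**The case against.** The strongest reply is that the time of collection is not the time of the condition. Many of the conditions in section 6.2.4 predate the visit: setting, organizational climate, stable patient characteristics, and the navigator contact before biopsy. An interview held later can ask about those earlier events. The reference period of the questions may be set in the patient survey and interview guide, which the appendix list gives by title only. This stands, and it limits the point. Late collection does not reverse such conditions; what remains for interview accounts of earlier events is the weaker problem of recall with the outcome known. It does not rescue the perception and knowledge measures, because the protocol text does not tie them to the pre-visit period.

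A second reply is that this is a small mixed-methods component of a pilot that triangulates its sources. That bears on how much weight the result will carry. It does not change the directional wording, which section 6.2.4 leaves unqualified.

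A third reply concerns remedy. Restricting the QCA to medical-record variables would remove the survey and interview inputs that Objective 2 exists to study. Some substitutes are nearly circular: plasma draw around the biopsy is what the intervention arranges, and usual care is asked not to arrange plasma testing before the initial visit (section 4.2). This also stands, and the fix below respects it.

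**Conclusion.** The point holds for patient perception and knowledge conditions. As written, the QCA would describe them as yielding an endpoint that was fixed up to about 19 weeks before they were measured, and it has no means of telling cause from consequence.

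Three stronger inferences are not supported:
- **That every QCA condition, or the whole QCA, is reversed.** Arm, site, demographics, setting and pre-biopsy process are not.
- **That the cut-offs will be crossed by reverse effect alone.** This depends on its size. The documents give no rates, and under the assumed 60% vs 30% the chance is only 0.16 for sufficiency.
- **That the trial's main result is affected.** The randomized intention-to-treat comparison in Objective 1 does not use these data.

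Nor does the 1-year window show that patients will be measured that late; it is an outer limit, and the section 4.3 schedule ends sooner. The conclusion assumes that no question period fixed elsewhere, for example in the interview guide, already ties these measures to the time before the visit. It is a modest point about interpretation, worth making because the correction is cheap.

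**What to change.** In section 6.2.4, before truth tables are built, classify each QCA condition as one of:

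- **Fixed before the endpoint visit:** arm, site, demographics, setting features, pre-biopsy navigator visit, and interview accounts of pre-visit events, the last flagged as recalled with the outcome known.
- **Post-visit perception or knowledge:** communication, treatment knowledge and beliefs, mistrust, satisfaction and similar measures.

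Then:
1. Reserve the statement that conditions "are necessary or sufficient to yield the primary endpoint" for the first class.
2. Report any configuration that includes the second class as associated with the endpoint and possibly a consequence of it.
3. Present the QCA with and without the second class.
4. Keep the survey and interview data in the analysis.
5. If plasma-draw timing is used as a condition, state that it is part of the intervention.

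The cost is a paragraph in the analysis plan, one extra field in the coding dictionary and a second QCA run. No new survey or data collection is needed. The downside is a narrower mechanistic claim.
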